<Study protocol with SAP>

**Locoregional recurrence after neoadjuvant versus adjuvant chemotherapy
based on tumor subtypes in patients with early-stage breast cancer: A
multi-institutional retrospective cohort study**

(Brief Title: Locoregional Recurrence After Neoadjuvant Versus Adjuvant Chemotherapy)

Version 1.0

Document Date: 2022-04-22

1. Research Hypothesis and Objectives

: The hypothesis of this study is to investigate whether there is a difference in ipsilateral breast recurrence between patients who received preoperative chemotherapy and those who received postoperative chemotherapy after breast-conserving surgery and radiation therapy for breast cancer. The objective is to conduct a multi-institutional retrospective analysis to examine this difference.

2. Criteria for Selection and Exclusion of Study Subjects

*Selection Criteria:

- Patients who underwent breast-conserving surgery for invasive breast cancer at three hospital in Korea between 2004 and 2018.

* Exclusion Criteria:

- Patients who underwent mastectomy.
- Patients who did not receive pre- or postoperative chemotherapy.
- Patients who did not undergo radiation therapy.
- Patients with bilateral breast cancer.
- Male breast cancer patients.
- Patients with secondary cancer.
- Metachronous or synchronous cancers.

3. Number of Study Subjects

- 10328 patients

4. Specific Research Methods

- Retrospective analysis of clinical information and pathological findings of patients who underwent breast-conserving surgery at the hospital from January 2004 to December 2018.
- Confirmation of ipsilateral recurrence in all patients, noting the date of recurrence if applicable, or the date of last outpatient visit or death if no recurrence occurred.
- Assessment of significant differences in IBTR-free survival rates between patients who received neoadjuvant chemotherapy (NAC) and those who received adjuvant chemotherapy (CTx).
- Subgroup analysis based on patient age, molecular subtype (Luminal A, Luminal B, HER2-enriched, basal-like), and clinical-pathological characteristics.

- Survival analysis conducted using the log-rank test and Cox proportional hazards model, with calculations made within a 95% confidence interval.

5. Data Collection Items

- Patient information: Age at the time of surgery.
- Surgical information: Date of surgery, type of breast-conserving surgery.

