- Pathological information: T stage, N stage, pathological complete response (pCR), hormone receptor status, HER2 receptor status, Ki-67%, histologic grade.
- Treatment information: NAC and chemotherapy regimen, hormone therapy, Herceptin administration.
- Prognostic information: Occurrence and date of local recurrence, occurrence date of other metastases or relapse, date of last outpatient follow-up

6. Informed consent

The requirement for informed consent was waived owing to the retrospective nature of the study.

7. IRB No.

- Seoul National University Hospital, 2204-074-1316
- Samsung Medical Center, 2023-09-076-001
- Boramae medical center, 10-2023-73

8. Statistical analysis plan

- Categorical variables are compared using Pearson's chi-square test.
- Continuous variables are compared using Mann-Whitney *U* and Kruskal-Wallis tests.
- Survival analysis would be conducted using the log-rank test with calculations made within a 95% confidence interval.
- Cox proportional hazards regression analysis are performed to adjust for related clinicopathological variables and estimate hazard ratios. Variables with a two-sided p-value of <0.05 in the univariate analysis would be included in the multivariate analysis, and those that showed a variance inflation factor of >4.0 in the multicollinearity test would be excluded. The model's goodness of fit was

evaluated using the Hosmer-Lemeshow test and a two-sided p-value of >0.05 indicated an appropriate model.

- The propensity scores are estimated using a logistic regression model, and 1:1 matching would be conducted using the greedy nearest-neighbor matching method without replacement using a caliper width of 0.10 standard deviation of the logit of the propensity scores. Variables that are differently distributed between the two groups were used for matching analysis. The standardized mean differences are calculated to evaluate the balance of variables between the two groups, and a value of <0.1 indicates an adequate balance.
- Missing data are treated using a complete case analysis approach.
- A two-sided p-value of <0.05 was considered significant.
- Analyses would be conducted using SPSS (version 26.0; SPSS Inc., IBM, Armonk, NY, USA) or R Statistical software (version 3.6.3; R Foundation for Statistical Computing, Vienna, Austria). Kaplan-Meier curves would be drawn using GraphPad Prism (version 10.0; GraphPad Software, San Diego, USA).

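### The Cox covariates are chosen by univariate p<0.05 and trimmed at VIF>4.0 with nothing forced in, so real confounders of the NAC comparison can be left out

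*Combined protocol and SAP*

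**What the plan says.** Section 8 (Statistical analysis plan) gives the purpose of the model: "Cox proportional hazards regression analysis are performed to adjust for related clinicopathological variables and estimate hazard ratios". Two data-driven rules then decide its content. The entry rule is "Variables with a two-sided p-value of <0.05 in the univariate analysis would be included in the multivariate analysis". The removal rule is that "those that showed a variance inflation factor of >4.0 in the multicollinearity test would be excluded".

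No covariate is named as mandatory, and nothing says that NAC versus adjuvant chemotherapy stays in whatever its own p-value or VIF. Section 5 lists the candidate items without marking any as required adjusters, for example "Pathological information: T stage, N stage, pathological complete response (pCR), hormone receptor status, HER2 receptor status, Ki-67%, histologic grade".

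Section 4 plans "Subgroup analysis based on patient age, molecular subtype (Luminal A, Luminal B, HER2-enriched, basal-like), and clinical-pathological characteristics". It does not say whether the screen is rerun within each subgroup.

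A separate 1:1 propensity match chooses covariates differently: "Variables that are differently distributed between the two groups were used for matching analysis". The plan does not say which analysis is primary.

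**The concern.** The comparison is retrospective and non-randomised, so the adjusted hazard ratio (HR) is only as good as its adjustment set. A confounder is related to both the choice of NAC and recurrence. The screen looks only at crude association with recurrence. If NAC lowers risk and is given more often to patients with a bad factor, that factor looks weaker on its own than it is. The screen is then most likely to drop the variable that the model most needs.

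Four consequences follow.

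- The chosen set depends on the number of events as well as on clinical relevance.
- If the screen is rerun by subtype, the subtype HRs may be adjusted for different variables and not be comparable, in a study framed around tumour subtypes.
- The VIF rule does not say whether one or both of a redundant pair leave.
- Read literally, a non-significant crude NAC effect would produce no adjusted NAC HR at all. The stated purpose suggests that the screen may be meant for covariates only, so this last point is an ambiguity to close.

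**Working it through.** **Inputs.** From the documents: 10328 patients (Section 3), two-sided 0.05, VIF limit 4.0 (Section 8), four subtypes (Section 4). The plan has no figure of its own to reproduce, because it gives no event count, NAC share or covariate distribution. Everything else below is assumed for illustration.

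**1. Chance that a real factor fails the screen.** With D events and prevalence 0.3, the test statistic has mean ln(HR)·√(D·0.3·0.7), and the drop probability is 1 − power. For HR 1.3 and D=300: 0.262·√63 = 2.08, giving a drop probability of 0.451.

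| Factor HR | D=100 | 300 | 500 | 662 |
|---|---|---|---|---|
| 1.3 | 0.775 | 0.451 | 0.233 | 0.129 |
| 1.5 | 0.541 | 0.104 | 0.014 | 0.002 |

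**2. Masking.** Take a 25% NAC share, a factor of HR 1.3 in 50% of NAC and 25% of adjuvant patients, and a true NAC HR of 0.70.

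- Overall prevalence is 0.25·0.50 + 0.75·0.25 = 0.3125.
- The NAC share is 0.125/0.3125 = 0.40 with the factor and 0.125/0.6875 = 0.182 without it.
- With rare events the crude HR of the factor is about 1.3·(0.40·0.7+0.60)/(0.182·0.7+0.818) = 1.3·0.880/0.945 = 1.21.
- At 300 events the mean is 0.191·√(300·0.3125·0.6875) = 1.53, so the drop probability is about 0.67. Without masking (NAC HR 1.0) it is about 0.44.

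Simulation agrees: 63%, 42% and 24% dropped at true NAC HR 0.7, 1.0 and 1.3.

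**3. Effect on the NAC HR.** Omitting one such factor multiplies the NAC HR by about (1+0.5·0.3)/(1+0.25·0.3) = 1.15/1.075 = 1.070. Omitting three independent ones multiplies it by 1.070³ = 1.22, taking 0.70 to about 0.86. The screen drops some and keeps others, so the result lies in between.

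Simulation: 10328 patients, three such confounders, exponential hazards, follow-up uniform on 4–18 years, 1000 cohorts per cell, NAC always kept in the model, Monte Carlo error about 2 points on coverage. With true NAC HR 0.70:

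| Events | Screened HR | Coverage | Fixed-set HR | Coverage |
|---|---|---|---|---|
| 100 | 0.776 | 90.9% | 0.688 | 95.5% |
| 300 | 0.750 | 91.2% | 0.695 | 95.3% |
| 660 | 0.724 | 90.3% | 0.702 | 93.3% |

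Power at 300 events is 50.7% screened and 69.8% fixed. In the screened model the mean standard error matched the empirical spread (0.145 and 0.144), so the under-coverage comes from bias. With true HR 1.0 the screened means were 1.086, 1.035 and 1.009; with true HR 1.3 they were 1.358, 1.311 and 1.295. With one confounder at 300 events, the screened HR was 0.721 with 94.0% coverage.

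A repeat with a constant-hazard Poisson model gave screened HRs of 0.775, 0.754 and 0.723 against a true 0.70. With a stronger imbalance (one HR 1.3 factor, 70% versus 20%, true NAC HR 0.75, about 510 events, 300 runs), the screen dropped the factor in 66% of runs. The mean HR was 0.80 against 0.75 when forced in, with coverage 87% against 97%.

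**4. Subtypes, if the screen is rerun in each.** Assume 300 events split equally, 75 per subtype. An HR 1.5 factor of 30% prevalence is dropped with probability 0.637 in each. All four models treat it alike with probability 0.637⁴ + 0.363⁴ = 0.18.

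**5. VIF rule.** VIF>4 means R²>0.75, or |r|>0.87 for a pair. For two binary variables VIF = 1/(1−φ²). With 60% hormone-receptor positive, 95% of them and no receptor-negative patients on hormone therapy, φ = 0.940 and VIF is 8.6 for both variables, so the literal rule removes both. At 85% uptake VIF is 3.3 and both stay. For HER2 status (20% positive) and trastuzumab, VIF is 3.4 at 75% uptake and 4.2 at 80%.

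**The case against.** The strongest reply is that the plan has a second adjustment that handles this scenario. Imbalances of 50% versus 25% in 10328 patients would always be detected (z of at least 19), so the matching rule would select every one of these confounders. Simulated exact 1:1 matching on them gave NAC HRs of 0.70, 0.70 and 0.69, with coverage of 94–95%. About 4,750 patients remained, and power at 300 events was 54% against 68% for the fixed set. This stands as a partial safeguard. It does not change the Cox HR, which would be reported beside the matched result with no stated order of priority.

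Second, the harm is concentrated. Material bias needs a protective NAC effect, several moderate confounders, and few or moderate events. There it hides a benefit and does not invent one. With true HR 1.0, simulated rejection rates were 5.4%, 4.6% and 3.2% at about 100, 300 and 650 events. At 660 events only about 3 points of the coverage shortfall come from the screen (90.3% against 93.3%). All of this stands and limits the weight of the point.

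Third, no bias was computed for the VIF rule, and if only one of a redundant pair leaves, the other largely carries its information. That is fair. However, the wording removes every variable over the limit, which can mean both.

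Finally, the subtype and treatment-exemption strands depend on readings that the text leaves open. They are wording to settle, not shown errors.

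**Conclusion.** The concern holds. The plan states a rule that selects on the wrong criterion for confounder control, and the main defect remains even if NAC is always kept in the model. The wording is certain; the size in this cohort is not. Under the assumptions above the bias ranges from negligible (true NAC HR 1.0 or 1.3 at 660 events) to a clear attenuation (0.70 reported as about 0.75, with 19 points of power lost, at 300 events with three confounders). The rule should be changed, but it does not by itself invalidate the study, because the log-rank test and the matched analysis do not depend on it.

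**What to change.** Replace both rules in Section 8 with text such as:

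> Every Cox model contains treatment group (NAC versus adjuvant chemotherapy) and a confounder set fixed in advance on clinical grounds: age at surgery, T and N stage as assessed before treatment where available, histologic grade, hormone receptor status, HER2 status, Ki-67 and grouped year of surgery, stratified by hospital. pCR is not in the set because it arises after NAC. No variable enters or leaves on its univariate p-value. VIF is reported as a diagnostic and never removes treatment group; redundant pairs are resolved in advance. Subtype HRs use the same set without the variables that define the subtype.

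If pre-treatment T or N is unavailable, report that as a limitation and do not substitute post-NAC stage. The minimum change is a named covariate list and a statement that treatment group always stays in.

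The cost is SAP wording and three data tasks. A hospital identifier must be recorded, since it is not a listed item. The existence of pre-treatment T and N must be confirmed, since Section 5 lists stage only under pathology. The missingness of Ki-67 and grade must be checked. Date of surgery is already collected.

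Intervals widen slightly: the mean standard error of the log HR was 0.150 against 0.145 in the 300-event, three-confounder simulation. The larger risk is lost patients, because "Missing data are treated using a complete case analysis approach". If Ki-67 or grade is often missing, forcing them in shrinks the analysed cohort and may select it.

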- The patterns of annual recurrence incidence would be drawn using the kernel smoothing method with the *ksmooth* function in R.

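### The Cox model is to be accepted on a Hosmer-Lemeshow p-value, which does not assess whether the NAC hazard ratio is constant over time, and no proportional-hazards check is planned

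*Combined protocol and SAP*

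**What the plan says.** Section 8 (Statistical analysis plan) gives the adjusted analysis in one bullet: "Cox proportional hazards regression analysis are performed to adjust for related clinicopathological variables and estimate hazard ratios". The same bullet goes on to variable selection and a variance-inflation screen. It ends with the acceptance rule, under which model fit is "evaluated using the Hosmer-Lemeshow test and a two-sided p-value of >0.05 indicated an appropriate model". The propensity-score logistic model comes only in the next bullet, with its own balance criterion (standardized mean difference below 0.1). There, "1:1 matching would be conducted using the greedy nearest-neighbor matching method without replacement".

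The outcome is defined in section 4 (Specific Research Methods), which records recurrence status by "noting the date of recurrence if applicable, or the date of last outpatient visit or death if no recurrence occurred". The cohort had "breast-conserving surgery at the hospital from January 2004 to December 2018".

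Two displays relate to time: "Kaplan-Meier curves would be drawn using GraphPad Prism", and "The patterns of annual recurrence incidence would be drawn using the kernel smoothing method". Neither is linked to the Cox model, and the text does not say that the smoothed curve is drawn by treatment group.

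**The concern.** The rule certifies the Cox model with a test made for another kind of outcome and another question. A single Cox HR summarises the NAC effect well only if the ratio of hazards is roughly constant over follow-up. Hosmer-Lemeshow compares observed with expected event counts across groups of predicted risk, and time does not enter the comparison. A pass therefore says almost nothing about that assumption. A p-value above 0.05 is also a failure to reject, not evidence that a model is adequate.

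The rule cannot be carried out unambiguously either. Patients censored early have no known yes/no outcome at a later date, and the plan gives no horizon, grouping or censoring-aware version of the test.

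At stake is how the adjusted HR is read. If NAC raised recurrence early and lowered it later, or the reverse, a single HR near 1 could be reported as no difference from a model labelled adequate.

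**Working it through.** **1. Which model the rule covers.** It closes the Cox bullet and comes before any logistic model is mentioned. As written it applies to the Cox model.

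**2. What else checks the model.** Sections 4 and 8 contain no Schoenfeld residuals, log-minus-log plot, time-by-treatment term or alternative estimate. The variance-inflation screen concerns collinearity only.

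**3. Spread of follow-up.** No data cut-off is stated. From the surgery window to the document date (22 April 2022), potential follow-up is 3.3 years (from 31 December 2018) to 18.3 years (from 1 January 2004). Two of the three ethics approval numbers carry 2023, for example "Samsung Medical Center, 2023-09-076-001". A cut-off at the end of 2023 would give 5.0 to 20.0 years.

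**4. What the test computes.** With g risk groups of size n, observed events O and expected events E, the statistic is Σ (O − E)² / [E(1 − E/n)], referred to chi-square on g − 2 degrees of freedom (8 for ten groups). Event times appear nowhere in it.

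**5. Why a changing effect passes.** Take an HR of 2.0 to year 3 and 0.7 afterwards (assumed). The ratio of cumulative hazards at c years is [2.0 × 3 + 0.7 × (c − 3)] / c:
- c = 4: 6.7 / 4 = 1.68
- c = 11: 11.6 / 11 = 1.05
- c = 18: 16.5 / 18 = 0.92

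Pooled over follow-up of 4 to 18 years, a yes/no analysis sees a ratio close to 1 and fits it with one coefficient.

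**6. Simulation (illustrative).** Only the 10,328 patients (section 3) come from the plan. Assumed: one prognostic covariate (log HR 0.5 per SD), censoring uniform over 4 to 18 years, and the NAC share and baseline hazard shown. There were 200 runs per row. Hosmer-Lemeshow (HL) used ten groups, on recurrence yes/no from a logistic model.

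| True NAC HR; NAC share; baseline hazard | Recurrences | HL p>0.05 | Single HR | HR to year 3 | HR after year 3 | Period-difference test p<0.05 |
|---|---|---|---|---|---|---|
| Constant 1.5; 25%; 0.5%/year | 687 | 96.5% | 1.50 | 1.51 | 1.50 | 5% |
| 2.0 then 0.7; 25%; 0.5%/year | 624 | 96.0% | 1.06 | 1.97 | 0.70 | 100% |
| 2.0 then 0.7; 25%; 1%/year | 1,194 | 96.0% | 1.08 | 1.99 | 0.70 | 100% |
| 2.0 then 0.7; 10%; 0.5%/year | 622 | 96.0% | 1.06 | 1.95 | 0.70 | 95% |
| 2.5 then 0.5; 50% of 4,000 patients; 0.7%/year | 335 | 92.5% | 1.07 | 2.52 | 0.49 | 100% |

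The Monte Carlo standard error near 96% is √(0.96 × 0.04 / 200) = 1.4 percentage points.

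**7. A wider set of assumptions.** This used 500 cohorts of 10,328 per setting, four covariates, both cut-offs in step 3, and 1:1 matching as in the plan.
- *HR 2.0 to year 3, then 0.5.* HL on yes/no rejected 3.8–6.2%, and HL on 5-year status 5.8–9.0%. The Schoenfeld test rejected 86–100% unmatched and 72–100% matched. The single HR averaged 0.86–1.02. Periods split at year 5, two years off the true change, still gave 1.38–1.47 and then 0.48–0.50.
- *Constant HR 1.3.* HL rejected 4.2–7.2% (yes/no) and 4.8–8.0% (5-year). Schoenfeld rejected 3.2–4.8% unmatched and 3.6–5.8% matched.
- *Where HL did react.* The 5-year version rejected 20–22% when the change fell exactly at year 5. With 4% yearly loss it rejected 20% under the reversal and 16% under a constant HR, so that rise mostly reflects censoring.
- *Milder change.* For 1.5 then 0.8, Schoenfeld rejected 67–71% unmatched and 49–54% matched at about 640 events. At about 284 events with 15% NAC it rejected 29% and 18%. For 1.5 then 1.0 it rejected 37% and 22%. HL stayed at 3.8–6.4% throughout.

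**The case against.** **The sentence may have been meant for the propensity model.** It may have been, but moving it would leave the Cox model with no check of fit at all.

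**No planned result depends on it.** This stands. The HR, its confidence interval, the log-rank test and the Kaplan-Meier comparison are the same with or without the rule, and no action is stated if the test fails. The cost is one reassuring sentence, not a wrong calculation.

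**The planned curves could reveal a reversal.** They could, if drawn by treatment group. They are descriptive, with no link to the Cox model, and grouping is not specified for the smoothed curve.

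**The simulations favour the point.** Partly true. A doubling followed by a halving is a chosen extreme. A yes/no analysis is nearly blind to timing by construction, so step 5 carries most of the argument. All 10,328 patients were treated as complete, whereas section 8 plans complete-case analysis, so the analysed number may be smaller. Subtype models will have fewer events still. The Schoenfeld test would then detect less than shown.

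**Stronger readings.** A reader might infer that hazards are non-proportional here and that the adjusted HR is therefore wrong. The documents contain no event data and support neither statement. A reader might also infer that the test breaks down in the matched analysis, because a model holding NAC alone yields only two predicted risks and 2 − 2 = 0 degrees of freedom. But the rule sits in the multivariable Cox bullet, and nothing applies it to a NAC-only matched model.

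**Conclusion.** The point holds on the text. The Cox model would be accepted on a test that does not address the assumption behind its HR, and nothing else in the plan addresses it. This is a stated rule that is wrong for its purpose, not just missing detail.

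The consequence is limited to false reassurance about the adjusted NAC HR. Its size cannot be taken from the documents, which give no event count, NAC share, expected HR, loss to follow-up or cut-off. Under the assumed scenarios, Hosmer-Lemeshow on recurrence yes/no passed a strongly changing effect about as often as a constant one, while the single HR sat near 1. Those figures show what could go unnoticed, not what is likely. The change should be made before analysis, because the adjusted HR answers the study's main question and the correction is cheap.

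**What to change.** Delete the Hosmer-Lemeshow sentence for the Cox model and replace it with wording to this effect:

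> Proportional hazards will be assessed with scaled Schoenfeld residuals (test and smoothed plot, shown whatever the p-value) for the NAC term, in the unmatched Cox model and in any Cox model fitted to the matched pairs, and for the covariates. NAC HRs for two follow-up periods, split at one cut-point fixed before analysis, will be reported alongside the single HR whatever the test result. The Cox model will be stratified on any covariate that clearly fails, or a time interaction for it will be added.

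The cut-point must be written into the SAP. The documents give no basis for a particular year. Potential follow-up may be as short as 3.3 years, so later cut-points leave fewer patients in the second period. If calibration is also wanted, name one censoring-aware test and its horizon.

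**Cost.** SAP wording and a few lines of R, which the plan already lists, with no new data. There is slightly more analysis and reporting, and period HRs are less precise than the single HR. Balance between matched groups is not assured among patients still at risk in the second period. The Schoenfeld test has limited power against mild departures (18–37% in the weaker settings above), which is why the plot and both period HRs are shown regardless.

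### Propensity matching and its balance check are specified only for the two overall groups, so subtype comparisons drawn from the matched set could be confounded without the SMD rule showing it

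*Combined protocol and SAP*

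**What the plan says.** The full title frames the comparison by tumor subtype, and Section 4 lists "Subgroup analysis based on patient age, molecular subtype (Luminal A, Luminal B, HER2-enriched, basal-like), and clinical-pathological characteristics".

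Section 8 sets out the matching in one bullet. "The propensity scores are estimated using a logistic regression model", and "1:1 matching would be conducted using the greedy nearest-neighbor matching method without replacement", with a caliper of 0.10 SD of the logit. Variables that differ between the two groups enter the match. Balance is judged by one rule: "The standardized mean differences are calculated to evaluate the balance of variables between the two groups, and a value of <0.1 indicates an adequate balance".

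Three things are not stated: any matching within or exactly on subtype, any subtype-by-covariate term in the score, and any SMD within a subtype. The plan also does not say whether subtype results come from the matched or the full cohort. Section 8 separately plans multivariable Cox regression, without linking it to the matched set or to the subtypes. Section 5 collects the relevant treatment data: "Treatment information: NAC and chemotherapy regimen, hormone therapy, Herceptin administration".

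**The concern.** Propensity matching balances covariates on average over the whole matched set. It does not make the members of a pair alike on each covariate. A patient with one subtype and advanced stage can be paired with a patient of another subtype and lower stage who has the same score. When such a set is split by subtype, the pairs break up and the overall balance need not carry over.

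If stage weighs more heavily in the choice of NAC in some subtypes than in others, a single main-effects score is wrong in each of them. The resulting imbalances can then offset one another in the overall SMD. At stake is a false pattern in which chemotherapy timing appears to matter differently by subtype.

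Herceptin use raises a related point. HER2-negative patients, taken here as not receiving it, pull the whole-cohort SMD towards zero, so it can understate a gap between arms among HER2-positive patients.

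**Working it through.** The plan has no figure to reproduce: it gives no arm split, subtype counts, event count or balance results. From the documents come N ("10328 patients", Section 3) and the algorithm, caliper and 0.1 threshold (Section 8). All other inputs below are assumptions.

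**1. Algebra.** For a binary covariate, SMD = (p1 − p0) / √{[p1(1 − p1) + p0(1 − p0)]/2}. Take two subtypes of equal size.
- 55% v 45% in one and 45% v 55% in the other: 0.10/√0.2475 = 0.20, so the SMDs are +0.20 and −0.20. Overall it is 50% v 50%, SMD 0.00.
- 60% v 40% and the reverse: 0.20/√0.24 = 0.41, so ±0.41. Overall SMD is again 0.00.

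**2. Simulation, one stage score.** Section 8 matching with a main-effects logistic score. Assumed subtype mix 35/25/15/25%, 40 runs per row. Order: Luminal A, Luminal B, HER2-enriched, basal-like.

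| Interaction | Log-odds of NAC per SD of stage | Mean within-subtype stage SMD |
|---|---|---|
| Strong | 1.2, 1.0, 0.4, 0.4 | +0.32, +0.24, −0.21, −0.18 |
| Moderate | 1.0, 0.9, 0.6, 0.6 | +0.14, +0.12, −0.10, −0.07 |
| Mild | 0.9, 0.85, 0.75, 0.75 | all below 0.05 in size |
| None | equal | all below 0.01 in size |

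A repeat of this design gave +0.37 to −0.23 under strong interaction, 0.10 to 0.18 in size under moderate, and at most 0.07 under mild. Its overall SMD was at or below 0.02, and about 70% of pairs crossed subtypes. A separate 20-run set with the strong log-odds and about 19% NAC gave +0.27, +0.23, −0.14 and −0.12, with overall SMD 0.03 and 67% of pairs crossing. The sizes therefore move with the other assumed inputs as well. Matching within subtype brought the SMDs to about 0.00 and kept 1,903 of 1,933 pairs in the 20-run set (30/1,933 = 1.6% lost).

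**3. Simulation, four covariates.** Assumed: 20% NAC, the same mix, covariates age, T, N and grade, and a main-effects score that includes subtype. Log-odds of NAC are 0.7 + m × (1, 0.3, −0.6, −1.1) for T and 0.8 + m × (0.8, 0.2, −0.4, −1) for N. T and N raise recurrence with log-HR 0.5 and 0.6. There is no true treatment effect. 40 runs per row.

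| m | Overall check passes | Some subtype SMD ≥0.1 | Spurious recurrence ratio, lowest to highest subtype | Some subtype SMD ≥0.1, matched within subtype | Pairs: overall, within subtype |
|---|---|---|---|---|---|
| 0 | 100% | 75% | 0.997 to 1.004 | 5% | 2,057, 2,047 |
| 0.25 | 100% | 95% | 0.945 to 1.05 | 8% | 2,064, 2,057 |
| 0.5 | 100% | 100% | 0.88 to 1.10 | 15% | 2,058, 2,043 |
| 0.75 | 100% | 100% | 0.87 to 1.08 | 18% | 2,014, 1,976 |

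The 75% at m = 0 is chance imbalance only, since the mean ratios are about 1.00. Under whole-cohort matching the overall ratio stayed at 0.99 to 1.00, and only 29% to 37% of pairs shared a subtype. Matching within subtype returned every subtype ratio to 1.00. The largest loss of pairs was 38/2,014 = 1.9%.

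**4. Herceptin.** Assume 25% are HER2-positive, of whom 80% v 65% by arm receive it.
- Whole cohort: 0.25 × 0.80 = 0.20 v 0.25 × 0.65 = 0.1625; SMD = 0.0375/0.385 = 0.097, which passes.
- HER2-positive only: 0.15/0.440 = 0.34.
- With 80% v 64%, the whole-cohort figures are 0.20 v 0.16, SMD 0.104, which fails.
- With 30% HER2-positive and 80% v 65%, they are 0.24 v 0.195, SMD 0.109, which fails.

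**The case against.** The strongest reply is that the plan never says its subtype results come from the matched set. Hazard ratios come from the Cox model, and Section 4 names that model directly after the subgroup bullet. T stage, N stage, grade and Herceptin use are all collected, so adjusted models within subtypes are possible. This stands in part: such models could remove some of the confounding. The plan does not commit to them, so the reply does not dispose of the point.

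The documents do not support four stronger readings that a reader might infer.
- **That subtype hazard ratios are confounded as the plan stands.** Systematic bias needs NAC selection to differ by subtype, and the documents have no data on that. Without such a difference, imbalance is chance alone.
- **That luminal and non-luminal groups will be biased in opposite directions.** That pattern follows from the assumed log-odds.
- **That the check is blind to Herceptin use.** It is diluted: slightly different inputs push the whole-cohort SMD over 0.1 and the rule flags them. Herceptin could also be a matching variable if it differs between the arms.
- **That subtype results are the study's main result.** The hypothesis and objective in Section 1 and the brief title concern the overall comparison. Subtype appears in the full title and as one of several subgroup factors in Section 4.

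**Conclusion.** The concern holds in conditional form. The plan has no step that secures or checks balance within the subtypes it undertakes to compare, and an overall SMD below 0.1 cannot stand in for one. That much is algebra and needs no assumed trial data.

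Whether it biases the subtype results depends on two things the documents leave open: whether those results use the matched set, and whether selection for NAC differs by subtype. Under strong interaction, within-subtype stage SMDs were mostly about 0.2 to 0.37 in size, and as low as 0.12 in one set of runs. Under moderate interaction they were about 0.10 to 0.18 (0.07 at the lowest), under mild at most 0.07, and under none about 0. In the four-covariate simulation the spurious recurrence ratios, before any Cox adjustment, were 0.945 to 1.05 at the weakest interaction and 0.87 to 1.10 at the stronger ones. This is a worthwhile improvement at low cost. It does not show that the subtype results are wrong.

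**What to change.** In Section 8:

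1. Match exactly on molecular subtype, with the propensity score fitted within each subtype or with subtype-by-covariate terms.
2. Report SMDs within each subtype against the 0.1 criterion. Where a covariate still exceeds 0.1, adjust for it in that subtype's Cox model.
3. State that subtype hazard ratios come from this within-subtype matched set.
4. Tabulate Herceptin use by arm among HER2-positive patients.

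The cost is SAP wording and a few lines of matching code, with no new data. The loss of matched pairs was at most about 2% in simulation, but would be larger if a subtype has few adjuvant controls. Some chance imbalance will remain in small subtypes: 5% to 18% of the four-covariate runs still had a subtype SMD of 0.1 or more, which is why step 2 says what to do then.
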